Cover Letter

Study Title: Nighttime Postural Care: Caregiver Training Program and Outcome Measure Feasibility

Principal Investigator: [name]

Date of Document: October 31, 2017; Updated April 15, 2018

Date Document Uploaded to ClinicalTrials.gov: March 2, 2021

St. Catherine University IRB Amendment request Form

Submit your Amendment Request Form for your protocol through Mentor IRB at the bottom of the protocol page.

Investigators may request approval to make amendments in various aspects of a project. All changes must be approved by the IRB prior to implementation. Amendments include: changes in experimental design, insertion of new information, correction of errors in text, change in primary investigator, change in study duration, change in numbers of subjects, or number of locations (site). Upon completion of review, an approval notification will be sent to the primary investigator.

Primary Investigator:

[name] **Date:** 4/15/18

Title of Research Proposal:

Protocol ID:

1. What are the proposed changes?

Design change: Instead of one group of participants with pre/post questionnaires and demonstration of positioning a mock client (mock client is one of the research investigators), the participants will be randomized into treatment group (receives the sleep care positioning 2-hour online education program) and control group/lesser intervention (handout with series of web links) groups.

Participants will be blinded to the two group design, however the control group will be informed they were in the control group after completing the "lesser" intervention, the post-questionnaire and the demonstration of sleep positioning with mock client. On the same day the control group will be given the option to complete the same educational package as the treatment group (2-hour online sleep care positioning program).

Participants will complete a 12-20 item quiz after educational intervention. Since the online sleep care positioning training program is being delivered via Brightspace D2L. Statistics from the quizzes will be collected. The quiz is a new addition. This information will be compared along with the results from the questionnaires and demonstration of positioning a person in the sleep system to better understand if the training program leads to learning and competence thus revealing more about the feasibility of the training program for use in future clinical intervention study.

Another change is that participants will only demonstrate the sleep positioning on a mock, rather than real client (i.e. person with CP, family member of research participant).

2. What is the rationale for proposed changes? The change results in a better research design. This randomized design will allow for a comparison group, allowing investigators to learn more about the merits of the educational (sleep care positioning training program) than would occur with only one pre/post group.

3. Do these changes either increase or decrease the benefits of this study?

If Yes, please explain: It'll increase the benefits of the study in that randomization into groups allows investigators to say that the educational intervention caused the learning (if learning occurs in the treatment group).

4. Do these changes either increase or decrease the risks or the risks of this study? If Yes, please explain and justify the increase in risk relative to the benefits: No, it does not increase risk to participants.

If the proposed changes require additional or changes to documents (such as the consent form), list these document titles.

One statement on the invitation to participate will change. I've also made formatting changes on the questionnaire and simulation observation instrument based on advice from a measurement consultant and based on new learning that occurred from a pilot test run that was recently completed. The script may also change slightly to adjust for changes. I spoke with [name] about the overall change in plans and I wasn't sure if IRB be needs to approve any and all changes (formatting and otherwise) to each document if the risks are not increasing or if minor changes to forms can be made without additional advance approval?

ST. CATHERINE UNIVERSITY REQUEST FOR APPROVAL FOR THE USE OF HUMAN SUBJECTS IN RESEARCH APPLICATION

IRB APPLICATION DOCUMENT CHECKLIST

The items listed below are the application, forms and supporting documents to be uploaded to Mentor IRB for your protocol/application submission. Consent forms and additional supporting documents may be uploaded to separately; see Mentor IRB Directions. For questions, contact the IRB Assistant at [contact] or [contact].

	IRB Application
	PI Documentation/CITI Training for Investigator(s)*
N/A	PI Documentation/CITI Training for Faculty Adviser (if applicable)*
	Informed consent form
N/A	Child assent form (if applicable)
	Recruiting materials (phone script, fliers, ads, etc)

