Research Questions. This project investigates both the feasibility of a sleep care positioning training protocol and the internal consistency reliability of the sleep disturbance scale for children (SDSC), a 26 item Likert-type rating scale developed by Bruni et al. in 1996 to evaluate sleep disturbances via caregiver report. Two Population Intervention Comparison Outcomes (PICO) questions will be addressed: 1. Is the training protocol feasible for use in training caregivers? 2. Does SDSC applied to children with cerebral palsy (CP) in the United States have sufficient internal consistency reliability for use in intervention research? Question one includes the following sub questions: A. Do caregivers have perceived competence and capacity to position children with CP (or similar mobility limitations) for sleep using sleep care positioning systems? B. Does the training protocol prepare caregivers to implement nighttime postural care (NTPC)?

Target Population. A convenience sample of 40 adult participants identified as professional or non-professional care providers (primarily from two community organizations that specialize in serving clients with CP) will be recruited for the study. Care providers of children with severe CP (those with limited ability to move and/or whom require use of a wheelchair) aged 6 to 12 are the primary target population, since this matches the intended sample of the future intervention study. However caregivers of children whom are outside of the 6-12 age range whom are candidates for NTPC and have similar mobility limitations as those with severe CP will not be excluded. Professional care providers might be nurses, occupational and physical therapists, assistive technology providers, etc. Non-professional care providers may be family members, care attendants, etc. Only individuals with knowledge of the child's sleep habits or routines will be included in the study

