This is a feasibility study. Feasibility studies are completed in advance of larger studies to better determine study design and are thought to help investigators avoid undesirable consequences from occurring when embarking on the larger studies (NIHR, 2017; Thaban et al., 2010). To understand the training protocol feasibility, data will be gathered from participants via questionnaire pre-training and post-training and via observational notes at the time of intervention simulation. Quantitative methods will be used to analyze numerical data and qualitative type methodology will be used to examine subjective data; however, the primary methodology of this study is quantitative.

Description of training protocol. All participants will receive the sleep care positioning training protocol with content on NTPC intervention implementation strategies. The primary topic areas include state of the evidence, outcome measurement, risk factor monitoring, and sleep care positioning methods and equipment. The content will be delivered using primarily electronic interactive tutorials, however some hands-on training may take place in person. Total training time is anticipated to require between 4 and 8 hours. Participants will simulate aspects of the intervention (with mock client, either researcher or actor) at the end of the training session. Additionally participants will be given the option of demonstrating aspects of the intervention with their own child (or child for whom they provide care) after completion of the training session and simulation.

Data Collection. Data will be collected to assess both the training protocol and the SDSC internal consistency reliability. To assess feasibility of the training protocol, data will be collected at baseline, post-training and post-simulation via questionnaire. The questionnaires (developed by investigators) contain Likert type rating scales and semi-structured questions about both participants' perceived competence to implement aspects of intervention and perceptions of the training protocol efficacy. A simulation observation instrument (developed by investigators) contains a structured format by which investigators can document observational notes of caregiver performance at time of intervention simulation. For this aspect of the study, raters will be trained by investigators to document observations of participant caregiver performance based on a set of criteria of competence.

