Internal consistency reliability of SDSC data will be collected during the training session. For this aspect of the study, a protocol will be issued to ensure consistent administration and scoring of the 26 idem assessment.

Data Analysis. Results of the training protocol and SDSC internal consistency reliability data will be analyzed. Data analysis of the feasibility of training protocol will be conducted using statistics for the numerical data and a systematic process of coding and theme identification for non-numerical data. Both within group and between group analyses will be conducted. Paired T-test statistics will be used to analyze changes that occur within groups pre-training vs. post-training, after calculating both total scores and sub scores of competence Likert scale ratings. Between group comparisons (comparing professional vs. non-professional) will be made using 2 sample T-test after calculating mean score change for each participant. Information provided by participants in response to open ended questions will be analyzed via a qualitative type coding process. Investigators will first code the data and analyze for themes independently and then discuss collectively. Any discrepancies will be resolved via discussion and

further examination of the data. Internal consistency reliability or how well test items measure the same construct, will be analyzed using Cronbach's Alpha.

d. Expectations of Participants: Give a step by step description of all procedures that you will have participants do. Attach any surveys, tests, instruments, interview questions, data collection forms, etc. that you will use with participants.

Participants will complete a baseline questionnaire to determine their level of knowledge or competence related to a select aspects of the NTPC intervention (i.e. state of the evidence, outcome measurement, sleep care positioning methods and equipment, & risk factor monitoring).

Participants will receive a 4-8 hour sleep care positioning training protocol. Participants will learn about various strategies used to implement NTPC and gain practice in assessments, positioning equipment and methods and development of risk monitoring plan. The content will be delivered primarily using electronic interactive tutorials and some in-person training. As a part of the training, participants will be asked to discuss and apply information relevant to their own child or client (if professional care provider).

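### No stratification by caregiver type, or adjustment for it, is described for a randomised sample of about 40 mixed caregivers whose quiz and demonstration have no baseline: a loss of precision, not a bias

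*Combined protocol and SAP*

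**What the plan says.** The amendment request form, item 1, replaces a single-group pre/post study with two arms: "the participants will be randomized into treatment group (receives the sleep care positioning 2-hour online education program) and control group/lesser intervention". The available text does not describe the allocation ratio, method, blocking, concealment or strata. The form's answer on benefits says that randomising will let the investigators attribute learning to the programme.

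Application section 1c, Target Population, defines who is randomised: "A convenience sample of 40 adult participants identified as professional or non-professional care providers". The two kinds differ in background: "Professional care providers might be nurses, occupational and physical therapists, assistive technology providers, etc", against "Non-professional care providers may be family members, care attendants, etc". Their expected numbers are not given.

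On timing, amendment item 1 adds the quiz: "Participants will complete a 12-20 item quiz after educational intervention". Section 1c places the demonstration after training ("Participants will simulate aspects of the intervention (with mock client, either researcher or actor) at the end of the training session"), and amendment item 1 places it after the handout for controls. Only the questionnaire has a pre-training measurement: "data will be collected at baseline, post-training and post-simulation via questionnaire".

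The one between-group test named in section 1c, Data Analysis, concerns caregiver type and not arm: "Between group comparisons (comparing professional vs. non-professional) will be made using 2 sample T-test after calculating mean score change for each participant".

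**The concern.** Caregiver type is known at enrolment and may well predict how someone performs when positioning a mock client or answering a quiz on positioning. For the questionnaire, a change score removes much of any starting difference. The quiz and the demonstration have no starting value to subtract. If one arm happens to receive more professionals, part of the observed arm difference on these two outcomes reflects who was allocated there. Neither the design nor the analysis, as described, separates that part out.

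A second consequence follows from the move to two arms. The professional v non-professional comparison of change was written when everyone received the same training. Applied to the randomised sample as it stands, it pools people who had the programme with people who had the handout. Unless both types are split alike between arms, it mixes caregiver type with intervention.

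At stake are the precision and credibility of the contrast on which the amendment rests its causal statement, and the meaning of the caregiver-type comparison.

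**Working it through.** **Inputs.** Total 40 (section 1c, Target Population; the amendment does not change it). Assumed, because the documents are silent: 20 per arm; 10, 20 or 30 professionals; professionals scoring δ = 0.5, 1.0 or 1.5 within-type SD higher; two-sided 5% tests; a numerical demonstration score; both arms taking the quiz. The documents contain no sample-size or balance calculation to reproduce.

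**1. Chance of imbalance.** With 20 professionals among 40, the number X in the treatment arm is hypergeometric: P(X = x) = C(20,x)·C(20,20−x)/C(40,20). This gives 0.24763 at x = 10, 0.20465 at x = 11 (and at 9), and 0.11512 at x = 12 (and at 8).

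- 12 v 8 or worse: 1 − 0.24763 − 2 × 0.20465 = 0.343. Half of this, 17%, favours treatment.
- 13 v 7 or worse: 0.34307 − 2 × 0.11512 = 0.113. Half, 5.6%, favours treatment.

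| Professionals of 40 | Arms differ by ≥ 20 points | ≥ 30 points | ≥ 40 points |
|---|---|---|---|
| 20 | 34% | 11% | 2.6% |
| 10 or 30 | 27% | 6.5% | 0.8% |

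**2. Shift in the arm difference.** Shift = (difference in share of professionals) × δ. For 13 v 7, the shares are 0.65 and 0.35, so the shift is 0.30δ = 0.15, 0.30 or 0.45 SD. For 12 v 8 it is 0.20δ = 0.10, 0.20 or 0.30 SD.

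**3. Error rates with no programme effect** (simulation, 200,000 trials per scenario, 20 professionals of 40).

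| δ | Unadjusted, all allocations, two-sided | Unadjusted, given 13 v 7 for treatment: falsely favours programme (nominal 2.5%) | Adjusted for caregiver type, same allocation, two-sided |
|---|---|---|---|
| 0.5 | 4.95% | 5.5% | 4.9% |
| 1.0 | 4.95% | 10.9% | 5.4% |
| 1.5 | 5.01% | 15.4% | 5.2% |

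Overall error is therefore intact. The excess appears only once a particular uneven allocation is in hand, and adjustment removes it.

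**4. Precision.** Left unadjusted, the outcome variance includes the gap between types: 1 + δ²·p(1−p). At p = 0.5 this is 1.06, 1.25 or 1.56, so the standard error is 3%, 12% or 25% larger than within types. This matters in a trial of 20 per arm, which has 80% power only for a difference of about 0.91 SD.

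**5. Caregiver-type comparison.** Suppose the programme adds Δ to questionnaire change relative to the handout. With a 13 v 7 split, 65% of professionals and 35% of non-professionals received the programme. The pooled contrast of change then moves by 0.65Δ − 0.35Δ = 0.30Δ, even if both types respond identically.

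**The case against.** The strongest reply is that randomisation already deals with this. Chance imbalance is not bias, an ordinary two-sample test allows for it, and the simulated overall error rate is 5%. That stands. A reader might infer that the arm comparison is biased or has inflated type I error; the design described does not support that. Only half of the imbalances could mimic a benefit, and the other half would hide one. The shift from a 13 v 7 split is also modest against the noise. The unadjusted standard error is √(2/20) × 1.03, 1.12 or 1.25 = 0.33, 0.35 or 0.40 SD, so the shift is about 0.5 to 1.1 standard errors.

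A reader might also infer that the sponsor decided against stratifying. The amendment is a short form that does not describe the method, and parts of the application are not in the available text. What can be said is that no stratification is described.

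Nor do the figures show that one arm is likely to contain almost no non-professionals. With 10 of them, the chance that an arm gets one or none is 0.8%. With 5 it is 34%, but stratification would then yield only 3 v 2, so recruitment would be the limit.

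The gap in performance is assumed, and its direction is not certain: professionals include technology providers as well as therapists, and the recruitment script presents the intervention as new. Finally, this is a feasibility study. That lowers the stakes, but the amendment introduced randomisation specifically to support a causal reading.

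**Conclusion.** The point holds as one of precision and clarity. As described, the plan neither balances nor adjusts for a factor that is known before allocation and already used in its own analysis, on two outcomes that lack a baseline. If half of the 40 are professionals and the arms are equal, there is about a one in three chance of a 12 v 8 split or worse and a one in nine chance of 13 v 7 or worse. The latter split would move the quiz or demonstration difference by 0.15 to 0.45 SD for assumed gaps of 0.5 to 1.5 SD. Both the caregiver mix and the gap are assumptions; with no gap between types, the arm comparison loses nothing.

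The pooling of arms in the professional v non-professional comparison does not depend on the assumed gap. It needs only an uneven split and a programme that works better than the handout.

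**What to change.** - **Amendment item 1:** state that randomisation is stratified by caregiver type (professional, non-professional), using concealed permuted blocks of varying size within each stratum.
- **Section 1c, Data Analysis, arm comparison:** compare programme with handout on the quiz and the demonstration using a linear model adjusted for caregiver type and the baseline questionnaire score.
- **Section 1c, Data Analysis, caregiver-type comparison:** make it within arm, or adjust it for arm.

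If allocation has already been done, the adjusted analyses alone address most of the problem.

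The cost is two allocation lists instead of one and one or two degrees of freedom (38 falls to 37 or 36 with 40 participants). In a small stratum the next assignment can be partly predictable if allocation is not concealed, which is why concealment and varying block sizes belong in the text. No extra participants, visits or measurements are needed.

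### Does the amendment leave the new quiz without a control-arm comparison?

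*Combined protocol and SAP*

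**What the plan says.** The quiz appears only in the IRB Amendment Request Form, item 1: "Participants will complete a 12-20 item quiz after educational intervention". The text continues: "Since the online sleep care positioning training program is being delivered via Brightspace D2L. Statistics from the quizzes will be collected". The next sentences call the quiz a new addition and say its results will be looked at together with those of the questionnaires and the positioning demonstration, to judge whether the training produces learning and competence.

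The same item describes the two arms. One receives the two-hour online program. The other is the "control group/lesser intervention (handout with series of web links) groups". Controls are told their allocation once they have finished the lesser "intervention, the post-questionnaire and the demonstration of sleep positioning with mock client". Then: "On the same day the control group will be given the option to complete the same educational package as the treatment group".

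Item 2 of the amendment gives the reason for the new design: to "learn more about the merits of the educational (sleep care positioning training program) than would occur with only one pre/post group". Item 3 says that randomization "allows investigators to say that the educational intervention caused the learning (if learning occurs in the treatment group").

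The application's section 1c (Target Population) plans "A convenience sample of 40 adult participants identified as professional or non-professional care providers". Section 1c (Data Analysis) describes paired and two-sample t-tests on the competence ratings. Its only between-group comparison is professional against non-professional caregivers, and it does not mention the quiz.

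**The concern.** The list of what controls finish before disclosure has three entries, and the quiz is not one of them. The quiz is instead tied to the *educational intervention*, and every other use of *education* or *educational* in the amendment refers to the treatment program. The quiz is also mentioned next to the platform that delivers that program. Read strictly, this leaves two unwelcome possibilities: controls take no quiz, or they take it only after choosing to do the program.

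Either would matter for the quiz. No baseline quiz is described, and the sample mixes professionals with family members and attendants. A post-program score in the treatment arm alone cannot separate learning from what people already knew. If controls were tested after the program, their scores would come from a self-selected group that had received the same teaching, so the contrast would say little about the program's effect. The causal claim in item 3 could then not be extended to the quiz.

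**Working it through.** The plan states no quiz test, target, effect size or allocation ratio, so there is no figure to reproduce. The check is a comparison of the texts.

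**1. The readings.**
- (a) Both arms take the quiz after their own allocated material.
- (b) Only people assigned to the program take it.
- (c) Controls take it after opting into the program.

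Under (a) no control score is affected. Under (b) or (c) no control has a score from before access to the program. With 40 participants and an assumed equal split, 40 / 2 = 20, so the number affected is 0 of 20 or 20 of 20. That restates the readings and does not help choose between them.

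**2. Use of *education/educational* in items 1 to 3 of the amendment.** There are five uses: the quiz sentence and four others. The four are the online program given to the treatment group, the package later offered to controls, the merits sentence in item 2 and the causal sentence in item 3. All 4 of 4 mean the treatment program. This favors (b) or (c). However, the package and the causal sentence carry their own qualifier, a mention of the treatment group, and item 2 names the training program in brackets. The quiz sentence has no such qualifier.

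**3. Use of *participants* in item 1 for the new design.** Apart from the quiz sentence there are three uses: participants are randomized, are blinded to the two-group design, and demonstrate positioning only on a mock client. All 3 of 3 cover both arms. Where one arm is meant (being told the allocation, being offered the program), the text says *control group*. By that pattern the quiz sentence covers both arms. This favors (a).

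**4. The disclosure sentence.** It says when controls are unblinded and is not a full visit schedule. It also omits the baseline questionnaire and the sleep scale, both of which are collected under section 1c (Data Collection). The quiz is introduced in the paragraph after it, as something new. Its absence from that sentence is weak evidence about timing.

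**5. The companion outcomes.** Item 1 sets the quiz beside the questionnaires and the demonstration as joint evidence on learning. For controls, the post-questionnaire and the demonstration come before disclosure. The sentence does not say that the comparison is between arms, but the grouping favors (a).

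**6. The platform sentence.** It is a grammatical fragment, and its plausible purpose is to explain why quiz statistics are available. Nothing says that controls cannot reach the quiz.

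**The case for a change.** The strongest case for acting is that item 3 uses the very phrase of the quiz sentence, *educational intervention*, and ties it to the treatment group. The handout is never described as educational. The questionnaires record perceived competence and opinions of the training, and the demonstration is documented by observers, so the quiz is the only item-scored knowledge test described. Staff running a same-day session could follow the wrong reading, and a control quiz taken after the program cannot be repaired in the analysis. Writing the order down would take a sentence or two.

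Part of this stands. The wording does not settle the order, nothing in the application resolves it, and a late control quiz could not be recovered. What does not stand is the step from unstated to wrong. No rule in the plan puts the control quiz after the program, and no stated analysis would give a misleading result. The causal statement in item 3 does not mention the quiz and can rest on the post-questionnaire and the demonstration, which are correctly placed. The same items say that the purpose of randomizing is to have a comparison group, and investigators with that purpose would test controls before offering them the program.

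**Conclusion.** No change follows. The amendment leaves out one detail: that controls take the quiz after the handout and before they are told their allocation and offered the program. Item 1 as a whole points to that order, and the design's stated purpose requires it if the quiz is to be compared between arms. Writing it down would record what sensible conduct already implies.

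The reach is one outcome, with no control score affected under the natural reading and all of them under the others. The post-questionnaire and the demonstration are untouched on any reading. No loss of power or bias can be put on the quiz, because the plan gives no quiz test, effect size or uptake of the program among controls.

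The conclusion assumes that the arm-neutral use of *participants* in item 1 carries through to the quiz sentence. It also assumes that nothing in the pages not available for review, such as the consent form, says otherwise.
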